### 13. STATISTICS

# 13.1. Statistical Analyses

### **13.1.1.** Sample Size Determination

It is expected that a study size of up to 250 subjects and duration of treatment up to 101 weeks will support the goal of 100 subjects completing one year of treatment.

### 13.1.2. Analysis Populations

### 13.1.2.1. Efficacy Populations

The efficacy analysis population will include all enrolled subjects who receive at least one dose of study drug and provide at least one post-enrollment MDS-UPDRS assessment.

MDS-UPDRS data will be summarized across study visits and include all available data. The baseline MDS-UPDRS scores will be from each subject's Screening Visit.

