### **Methodology:**

The safety analysis population will include all enrolled subjects who receive at least one dose of study drug. Safety data will be summarized from the time of first dose and include all available safety data. No formal statistical testing will be done.

All AE data will be listed and will be summarized by system organ class, preferred term, and analysis group, as well as for all analysis groups combined. Quantitative safety variables (e.g., vital signs and clinical laboratory tests) will be summarized at each visit by analysis group, as well as for all analysis groups combined and changes from baseline will be summarized by analysis group at selected visits.

The efficacy analysis population will include all enrolled subjects who receive at least one dose of study drug and provide at least one post-enrollment MDS-UPDRS assessment.

MDS-UPDRS, Part IV and Combined Score, Parts I, II, and III data will be summarized across study visits and include all available data. The baseline MDS-UPDRS scores for a subject will be their MDS-UPDRS scores from the Screening Visit.

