The underlying cause of LID is unknown, but the pulsatile administration of levodopa treatment and the degree of denervation in the striatum appear to influence its development (Del Sorbo et al., 2008). Other factors that have been associated with a higher incidence and severity of LID include early age of onset of PD, longer duration of levodopa treatment, levodopa total exposure, female gender, and genetic factors. The preferential use of dopamine agonists in the treatment of early disease and the careful management of pulsatile effects of levodopa therapy can delay but not eliminate the development of LID.

Amantadine IR, which is approved for the treatment of PD, is used off-label by movement disorder specialists and other neurologists to treat LID in patients with PD. A number of literature reports suggest amantadine is effective for the treatment of LID (Verhagen et al., 1998; Verhagen et al., 1999; Luginger et al., 2000; Snow et al., 2000; Paci et al. 2001; Thomas et al., 2004; da Silva-Junior et al., 2005; Sawada et al., 2010; Wolf et al., 2010; Goetz et al., 2013).

Despite amantadine's reported utility in the treatment of LID, until recently, the drug was not extensively studied in well-controlled clinical trials that meet evidence-based clinical or regulatory standards of acceptance, nor was the optimal dose for this indication established. The majority of patients with PD tolerate 200 mg/day of the amantadine IR formulation; however, the available literature on amantadine for the treatment of LID indicates that higher doses of amantadine produce a greater reduction in LID symptoms (Verhagen et al., 1998; Luginger et al., 2000). However, the increased frequency of adverse events (AEs) at higher doses, in particular central nervous system (CNS) events and sleep disturbances, limits the routine use of amantadine

Page 20 of 74

IR at doses of 300 mg/day or higher (Tyrrell et al., 1964; Jackson et al., 1967; Hayden et al., 1981).

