### 4.2. Dose and Dose Regimen Justification

The proposed dose of amantadine HCl in ADS-5102 is 340 mg, to be taken once nightly at bedtime. The  $t_{max}$  for ADS-5102 is expected to occur at 12 to 14 hours post dose. ADS-5102 is designed to achieve maximal concentrations in the early morning through mid-day, when LID tends to be troublesome, and lower concentrations in the evening, potentially reducing the negative impact of amantadine on sleep. This pharmacokinetic profile could enable higher daily doses to be tolerated with a once-nightly ER preparation than can be tolerated with an IR formulation. The once-nightly dosing regimen may also provide enhanced convenience and improve compliance. The labeled dose of Symmetrel for initiating treatment of PD is 100 mg given twice daily. The label also allows for an increase of up to 400 mg daily in divided doses for patients whose responses are not optimal with 200 mg daily. Figure 1 shows pharmacokinetic modeling of the steady state exposure for the ADS-5102 formulation compared to the approved doses of amantadine IR. Profiles were generated from Adamas clinical data in healthy volunteers (NPI-5103-C101).

Figure 1: Pharmacokinetic Modeling of Steady-state Concentrations for ADS-5102 vs **Approved Doses of Amantadine IR** 

ADS-5102 administered as 340 mg once-nightly results in a PK profile that provides higher exposures than possible with 100 mg bid amantadine IR, and yet remains within those approved in the Symmetrel package insert. As seen in Figure 1, the Cmax of the recommended dose of ADS-5102 remains below that of the 200 mg amantadine IR bid. The minimal concentration after dosing with ADS-5102 remains above the Cmax from a 100 mg dose of amantadine IR.

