#### 5.2. **Secondary Objectives**

To evaluate duration of ADS-5102 effect on dyskinesia as assessed by the Unified Parkinson's Disease Rating Scale (MDS-UPDRS), Part IV.

To evaluate clinical progression of Parkinson's disease as assessed by MDS-UPDRS, Combined Score, Parts I, II, and III.

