**Table 4: Efficacy Assessments** 

Assessment	Study Visit	Description
MDS-UPDRS	Screening Week 8 Week 16 Week 28 Week 40 Week 52 Week 64 Week 76 Week 88 Week 100 (or ET)	The MDS-UPDRS has 4 parts: Part I (non-motor experiences of daily living), Part II (motor experiences of daily living), Part III (motor examination), and Part IV (motor complications)

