#### 11.1. Screening/Day -14 to -1

During screening, potential subjects for the study will be fully informed about the nature of the study and possible adverse events (AEs). Subjects who wish to participate in the study must read and understand the consent form and sign the document after the investigator has answered all questions to the candidate's satisfaction. Further procedures can begin only after the consent form has been signed.

The Screening Visit must be conducted within 14 days prior to Day 1.

NOTE: If a subject from a previous Adamas LID study wishes to enroll directly in ADS-AMT-PD302 without a time gap, they should have their Screening Visit (Visit 1), including consent, for the ADS-AMT-PD302 study occur during the final efficacy study visit for the previous Adamas efficacy study, as outlined in the previous protocol.

Per the Schedule of Events in Appendix A, if a subject is directly rolling over to the open label extension, a number of common assessments between the Adamas efficacy study visit and the Screening Visit (ADS-AMT-PD302) only need to be performed once.

Potential study subjects will be evaluated for entry into the study according to the stated inclusion and exclusion criteria. Individuals who are identified during this screening as not eligible for study enrollment need not complete all screening procedures. The reason for ineligible status is to be documented.

The following procedures will be performed to establish each subject's qualifications for enrollment into the study:

- The subject is fully informed about the study and gives written informed consent to participate in the study;
- Confirm commitment of caregiver and/or study partner, if applicable;
- Review inclusion/exclusion criteria and evaluate initial subject eligibility;
- Record demographic information;

- Vital signs (standing blood pressure), assessment of orthostatic hypotension should occur at screening visit and apply only to ADS-AMT-PD302;
- Medical history with an emphasis on the subject's Parkinson's disease and movement disorders, including dyskinesia and past treatments for these conditions; alcohol and drug use, other neurological diseases, psychiatric disorders including Major Depressive Disorder or symptom (e.g., hallucinations, agitation, paranoia), history of seizures, stroke or TIA; history of MI or CHF; and history of cancer;

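### For subjects not on amantadine at Screening, change in MDS-UPDRS Parts I–III from the Screening baseline is net on-treatment change, not PD progression; a within-subject change from Week 8 should be added

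*Protocol*

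**What the plan says.** Protocol 5.2 lists two secondary objectives: duration of effect on dyskinesia (MDS-UPDRS Part IV) and "To evaluate clinical progression of Parkinson's disease as assessed by MDS-UPDRS, Combined Score, Parts I, II, and III".

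Protocol 13.1.2.1 gives a single baseline for the scale, "The baseline MDS-UPDRS scores will be from each subject's Screening Visit", and the Synopsis (Methodology) repeats it: "The baseline MDS-UPDRS scores for a subject will be their MDS-UPDRS scores from the Screening Visit". Both places otherwise say only that MDS-UPDRS data are summarized by visit using all available data.

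On timing, Protocol 11.1 states: "The Screening Visit must be conducted within 14 days prior to Day 1". For Group 1, who roll over without a gap, Screening is to "occur during the final efficacy study visit for the previous Adamas efficacy study, as outlined in the previous protocol". Groups 2 and 3 have no visit overlap with a previous protocol (Protocol 6.1). Their inclusion criteria admit subjects whose dyskinesia is being managed with amantadine at entry (Protocol 7.1.2 and 7.1.3).

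The visit list in Protocol Table 4 begins "Screening Week 8 Week 16 Week 28" and runs to Week 100 or early termination. There is no MDS-UPDRS at Week 4 or at the safety follow-up visit.

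On the drug, Protocol 4 says: "Amantadine IR, which is approved for the treatment of PD, is used off-label by movement disorder specialists". Protocol 4.2 adds that 340 mg ADS-5102 "provides higher exposures than possible with 100 mg bid amantadine IR", the latter being the labelled starting regimen for PD.

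**The concern.** A pre-drug reference suits Part IV in a subject starting treatment, because the question there is what the drug does to dyskinesia. Progression on Parts I–III is a different question. If the drug improves those scores, a subject starting it takes a one-off step down between Screening and the first on-drug score, and progression then runs up from the lower level. Change from Screening adds the two together. The step does not fade with follow-up: it is subtracted at every later visit.

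The Screening score also means different things in different subjects. Ex-placebo Group 1 subjects, and Group 2 and 3 subjects not taking amantadine, are scored without the drug. Ex-active Group 1 subjects are scored at the feeder study's final efficacy visit, with the ADS-5102 effect already present. Group 2 and 3 subjects on other amantadine lie somewhere between. A change summarized over all of them would not estimate one quantity.

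At stake is the second secondary objective. A flat or improving change from Screening could be read as absence of progression when scores are worsening on treatment.

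**Working it through.** The plan states no progression rate, symptomatic effect or MDS-UPDRS variance, so there is no planned figure to reproduce. The check is algebra with assumed inputs.

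**From the documents**
- Baseline is Screening (Protocol 13.1.2.1), up to 14 days before Day 1 (Protocol 11.1).
- The first scheduled on-drug score is at Week 8 (Protocol Table 4). The 340 mg dose starts in Week 2 (Protocol Table 3), so a subject on schedule has had about seven weeks at that dose.
- The last scheduled on-drug score is at Week 100.

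**Assumed**
- P, progression on Parts I–III: 2, 3 or 5 points a year.
- S, one-off symptomatic improvement on starting the drug, complete by Week 8 and stable afterwards: 0, 2, 4 or 6 points.
- f, the share of summarized subjects whose Screening score carries no amantadine effect. f = 1 describes the affected subjects alone.

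**Change from Screening**
- Expected change at t years = P × t − f × S.
- Share of progression hidden = f × S / (P × t).
- At Week 100, t = 100/52 = 1.92 years, so true progression is 3.85, 5.77 or 9.62 points.

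For affected subjects (f = 1), the measured Week-100 change and the share hidden are:

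| Step S | P = 2 (true 3.85) | P = 3 (true 5.77) | P = 5 (true 9.62) |
|---|---|---|---|
| 0 | 3.85 (0%) | 5.77 (0%) | 9.62 (0%) |
| 2 | 1.85 (52%) | 3.77 (35%) | 7.62 (21%) |
| 4 | −0.15 (104%) | 1.77 (69%) | 5.62 (42%) |
| 6 | −2.15 (156%) | −0.23 (104%) | 3.62 (62%) |

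The range is 0% to 156%. Above 100%, a worsening subject appears to improve.

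In a mixed summary the shortfall scales with f. For P = 3, S = 4 and f = 0.5 it is 0.5 × 4 = 2 points, so 3.77 is measured against a true 5.77 (35% hidden). The documents do not give f. The 1:1 randomization of ADS-AMT-PD301 (SAP 3) indicates that Group 1 can include both ex-placebo and ex-active subjects.

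**Change from Week 8**
- Expected change = P × (t − 8/52). S and f drop out, given the stability assumption.
- Weeks 8 to 100: 92/52 = 1.77 years, giving 3.54, 5.31 or 8.85 points for P = 2, 3 or 5, whatever the step.
- Weeks 8 to 52: 44/52 = 0.85 years, giving 1.69, 2.54 or 4.23 points.

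Divided by elapsed time, each returns the assumed rate.

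**The case against.** Several counter-arguments carry weight.

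- **No change statistic is stated.** A reader might infer that the plan measures progression as change from Screening. It does not say so. The Synopsis mentions changes from baseline only for quantitative safety variables. This stands, and the point is therefore conditional. Still, a defined baseline has little purpose except change from it.
- **The ADS-AMT-PD302 study SAP was not supplied.** SAP 7.1 refers derivations to the study SAPs. The SAP supplied is an integrated safety plan that uses MDS-UPDRS only as a baseline characteristic (SAP 8.6). This stands: the study SAP may already deal with the matter.
- **Visit summaries would show worsening after Week 8.** Partly right, because the Week 8 score is collected and summarized. But Protocol 13.1.3 summarizes observed data without imputation, so visit means come from changing sets of subjects and do not replace a within-subject contrast.
- **Pooling is not specified.** A reader might infer a single pooled progression figure that cannot be interpreted. The efficacy text neither pools nor splits, so that reading goes too far. What holds is that a combined summary, if produced, would mix baselines.
- **Not every subject is affected.** Correct: ex-active Group 1 subjects and those on amantadine at Screening are affected less or not at all.
- **The effect may be nil.** Approval of immediate-release amantadine for PD gives no effect size for ADS-5102 on Parts I–III in levodopa-treated subjects with dyskinesia. This stands, and is why the table starts at a zero step.
- **A Week 8 reference does not isolate progression.** PD medication may be changed freely (Synopsis, dosing regimen) and subjects will drop out. This stands as a limit on the fix.

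**Conclusion.** The point holds in a limited form. Measured from the one baseline the protocol defines, change in Parts I–III is net on-treatment change, not progression, for ex-placebo Group 1 subjects and for Group 2 and 3 subjects not on amantadine at Screening. For the others, Screening already carries some or all of the drug's effect.

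The direction is an inference from the protocol's own statement about amantadine in PD. The size cannot be fixed from the documents: 0% to 156% of Week-100 progression in affected subjects, under the assumed steps and rates, and proportionately less in a mixed group. A reader might infer that some masking is certain. The documents do not support that, because a zero step is not excluded.

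This concerns a descriptive secondary objective in an open-label study whose primary objective is safety. It is an inexpensive improvement that helps the study answer its own question, not a flaw in the main result.

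**What to change.** For the progression objective only (Parts I–III Combined Score), in the protocol's statistics section or the ADS-AMT-PD302 study SAP:

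1. Add within-subject change from Week 8 to Weeks 52 and 100, with 95% CI.
2. Show it by amantadine exposure at Screening: continuing ADS-5102, other amantadine, none. Feeder-study treatment assignment and the medication record required by Protocol 8.8 should supply the classification.
3. Label change from Screening as net on-treatment change.
4. Keep Screening as the Part IV baseline.

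A random-slope model over Weeks 8 to 100 is an optional extra.

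The cost is some plan wording and one more summary of scheduled data; no visit or assessment is added. There are three downsides. Subjects without a Week 8 score leave this summary. It assumes the symptomatic effect is stable from Week 8 onward. PD medication changes and dropout still confound it, so the report should say that it removes one source of bias and not all of them.

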# 13.1.3. Handling of Missing Data

Observed data will be summarized. There will be no imputation of missing data.

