#### 6.2. **Number of Subjects**

Up to 250 (all active) will be enrolled at approximately 90 sites worldwide.

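### Duration of effect to Week 100 is summarized from observed cases only; departures tied to fading benefit could flatten the curve, and a cheap added analysis would help to show it

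*Protocol*

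**What the plan says.** The first secondary objective (Protocol Section 5.2) is "To evaluate duration of ADS-5102 effect on dyskinesia as assessed by the Unified Parkinson's Disease Rating Scale (MDS-UPDRS), Part IV". The second is clinical progression on Parts I to III combined.

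The analysis of both is one sentence in Section 13.1.2.1: "MDS-UPDRS data will be summarized across study visits and include all available data". The Synopsis (Methodology) says the same. Section 13.1.3 adds: "Observed data will be summarized. There will be no imputation of missing data". The efficacy population needs one dose and that the subject "provide at least one post-enrollment MDS-UPDRS assessment". No longitudinal model, completer comparison, display by time of departure or missing-data sensitivity analysis is named.

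On size, Section 6.2 says "Up to 250 (all active) will be enrolled at approximately 90 sites worldwide". Section 13.1.1 repeats the enrolment ceiling of 250, gives the 101-week limit on dosing, and says only that these "will support the goal of 100 subjects completing one year of treatment". No dropout rate is given, and Section 7.3 does not replace leavers.

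An MDS-UPDRS is taken at early termination (Sections 6.1 and 11.14). Table 4 lists it in the same row as Week 100, and no analysis rule says where it is counted. The supplied SAP covers the integrated summary of safety. It uses the MDS-UPDRS only as a baseline characteristic (SAP Section 8.6).

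**The concern.** An observed-case mean at a late visit describes the subjects who are still there. If those whose dyskinesia benefit fades tend to leave, later means lean towards subjects who still respond. The trend across visits then mixes change within subjects with change in who is observed. A flat curve would be read as a lasting effect when it could partly be selection.

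Several features of this design make that hard to see:

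- There is no control arm whose curve could reveal selection.
- No MDS-UPDRS is scheduled after the early termination visit.
- Signs of lack of efficacy are generally not recorded as adverse events (Section 12.1.1).
- Neither the reasons listed in Section 7.5 nor the shell of SAP Table 1.1.2 has a lack-of-efficacy category.

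At stake is the interpretation of durability. No hypothesis test is planned for it, so no error rate is affected.

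**Working it through.** **1. The plan's own figure.** From Section 13.1.1, 100 / 250 = 0.40 retained, so the goal is still met with a loss of 1 − 0.40 = 60% by one year if 250 enrol. In reverse, 100 / (1 − 0.60) = 250. Since no dropout rate is stated, 250 cannot be derived from the protocol's inputs. The enrolment needed for 100 completers would be 125, 143, 167, 200 or 250 at an assumed dropout of 20, 30, 40, 50 or 60%. If the 60% hazard continued to Week 100 (an assumption), 0.40^(100/52) = 0.17 would remain, about 43 of 250.

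**2. Closed form.** Let r be the share retained, z_r the standard normal quantile of r, φ the normal density, and ρ the correlation between staying and benefit. Then the bias towards apparent benefit, in SD units, is ρ·φ(z_r)/r. At r = 0.40, z_r = −0.253 and φ = 0.386, so φ/r = 0.966; ρ = 0.3 gives 0.29.

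| Retained | ρ = 0.1 | ρ = 0.3 | ρ = 0.5 | ρ = 0.7 |
|---|---|---|---|---|
| 80% | 0.03 | 0.10 | 0.17 | 0.24 |
| 60% | 0.06 | 0.19 | 0.32 | 0.45 |
| 40% | 0.10 | 0.29 | 0.48 | 0.68 |
| 17% | 0.15 | 0.44 | 0.74 | 1.04 |

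The documents give neither ρ nor an SD. At ρ = 0 the bias is zero.

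A two-class picture shows the same thing. Suppose half keep a 4-point benefit and half have lost it, so the true mean is −2, with 40% retained overall. Retention of 50% against 30% gives (0.5 × −4)/(0.5 + 0.3) = −2.5. Retention of 60% against 20% gives −3.0, and 70% against 10% gives −3.5.

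**3. Simulation, early-termination scores left out.** All inputs are assumed: 400 trials of 250; mean Part IV change −4 at Week 8 fading to −2 at Week 100; random intercept SD 3, random slope SD 2, error SD 2, so the SD at Week 100 is √(9 + 4 + 4) = 4.1; dropout driven by the last observed change.

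| Retained at Week 100 | Observed-case bias (points) | Share of the 2-point fade |
|---|---|---|
| 55% | −0.73 | 37% |
| 42% | −1.06 | 53% |
| 51% | −1.42 | 71% |
| 40% | −1.86 | 93% |

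The order is not monotone in retention because the strength of the dropout link also varies. A repeat with similar inputs and 46% to 58% retained gave −0.65 to −1.57. Sequential regression on earlier visits, which is valid under missing at random, was within ±0.03.

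**4. Other inputs.** Here the true change goes from −3 at Week 8 to −1 at Week 100, with 26% to 29% retained at Week 100.

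| Dropout depends on | Observed-case, Week 100 | Missing-at-random analysis, Week 100 |
|---|---|---|
| Nothing related to response | −0.99 | −0.98 |
| Last observed score, moderate | −1.96 | −0.98 |
| Last observed score, strong | −2.63 | −1.01 |
| Unseen current score, moderate | −2.12 | −1.31 |
| Unseen current score, strong | −2.89 | −1.68 |

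At Week 52 the truth was −2.04, and the observed-case mean was −2.47 (moderate) or −2.86 (strong) when dropout followed the last score. The bias there is −0.43 or −0.82, against −0.96 or −1.63 at Week 100.

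**5. Pooling early-termination scores into Week 100.** Take the fade in step 3, dropout unrelated to response, half retained, and leavers' last scores centred on the midpoint, Week 54 (an assumption). Leavers average −4 + 2 × (46/92) = −3. The pooled mean is (−2 − 3)/2 = −2.5, a bias of −0.5 where leaving them out gives none. A simulation of the unrelated case gave −0.59. With dropout linked to response, pooling left −0.5 to −0.83 across two runs.

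**The case against.** The case on the other side has several parts.

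- **A study SAP may deal with it.** SAP Section 7.1 refers to study SAPs, which are not among the documents. This stands: the gap is shown for the protocol, not for everything the sponsor wrote.
- **Early-termination scores are collected and count as available data.** This also stands, and it means the 37% to 93% in step 3 is a case without those scores. It does not rescue the summary. Pooled at Week 100 they mix early scores with two-year scores (step 5), and they leave the intermediate visits as they were.
- **The link between fading benefit and leaving is assumed.** The documents do not assert it. Listed reasons for stopping, such as falling eGFR, adverse events or an excluded medication, need not track Part IV. If dropout is unrelated to response, there is no bias.
- **The accuracy of the missing-at-random analysis is built into the simulation.** This is correct, and the check used sequential regression and not the mixed model itself. Step 4 shows the residual error when dropout depends on unseen scores, although it is smaller than that of the observed-case mean.
- **The simulated course is too uniform.** Baseline is the Screening score. Group 1 is screened at the final efficacy visit of the previous study, so former active subjects may be on drug. Groups 2 and 3 may enter on amantadine. This stands, and it affects how the model should be specified.
- **The objective is secondary and descriptive.** This is true and limits the weight of the point.

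**Conclusion.** The point holds as a cheap improvement. The protocol's only analysis of two secondary objectives cannot separate a lasting effect from selective departure, and the data to examine this are already collected. The direction of the bias is clear if fading benefit leads to departure; the size is not known. The figure of roughly 0.7 to 1.9 points at Week 100 rests on an assumed 2-point fade, SD about 4, roughly half retained, dropout driven by the last observed score, and early-termination scores left out.

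A reader might infer four stronger things that the documents do not support:

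- **That the sponsor plans for 60% dropout.** That figure is only what 100 out of a maximum of 250 allows.
- **That a flat curve would be a selection artefact.** It could be, but neither dropout nor its link to response is known.
- **That declining to impute is itself the error.** A likelihood-based model needs no imputation and is compatible with that sentence.
- **That removing dropout bias would isolate the drug effect.** With no control arm and PD medication changes allowed, it would not.

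**What to change.** Keep the observed-case table. Add to Sections 13.1.2 and 13.1.3, or to the study SAP:

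1. A likelihood-based repeated-measures analysis of change from baseline in Part IV, and in Parts I to III combined, with visit, baseline and entry group. Split Group 1 by prior treatment (placebo or active). Place early-termination scores at their actual time and do not pool them into Week 100.
2. Observed-case curves by time of departure: left before Week 52, reached Week 52, reached Week 100.
3. A simple missing-not-at-random sensitivity analysis, such as a delta shift applied after dropout.

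The cost is a paragraph of analysis text and modest programming, with no new data. The main analysis would rely on missing at random, which items 2 and 3 help to check.
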